#### 9.4.3 ANALYSIS OF THE SECONDARY ENDPOINT(S)

To analyze USSQ findings between study arms (secondary endpoint), Mann-Whitney U test or independent t-tests will be used for comparisons of continuous variables and chi-square or fishers exact test for comparisons of categorical variables.

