### 1.3 SCHEDULE OF ACTIVITIES (SOA)

| Procedures                            | Screening/Enrollment
Day -90 to -1 | Stent Placement
(Day 0)         | Post-Stenting, Visit 1
(Day 1) | Follow up Phone call
(Day 3)  | Stent Removal
(Day 7-10) | 2-days Post Stent
Removal
(Day 9-12) |
|---------------------------------------|---------------------------------------|------------------------------------|-----------------------------------|----------------------------------|-----------------------------|--|
| Informed consent                      | X                                     |                                    |                                   |                                  |                             |  |
| Demographics                          | X                                     |                                    |                                   |                                  |                             |  |
| Medication Review                     | X                                     | X                                  | X                                 | X                                | X                           | X  |
| Randomization                         |                                       | X                                  |                                   |                                  |                             |  |
| Ureteral Stent Symptoms Questionnaire |                                       |                                    | X                                 | X                                | X                           | X  |
| RELIEF Ureteral Stent or DJ Stent     |                                       | X (placement per standard of care) |                                   | X (removal per standard of care) |                             |  |
| Intraoperative Post Stent Photo       |                                       | X                                  |                                   |                                  | X                           |  |
| Adverse event review and evaluation   |                                       | X                                  | X                                 | X                                | X                           | X  |

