**Secondary Objectives:**

- Assessment of pain or irritative symptoms attributed to the ureteral stent as well as unplanned return visits to ED, OR, or clinic.
- Reporting the Ureteral Stent Symptoms Questionnaire (USSQ) before stent placement, after placement at day 3, prior to removal and post removal.
- Visualization of distal coil floating in bladder (Y/N), after stent placement.

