**Study Endpoints:****1- Primary effectiveness endpoint:**

- Study success defined as adequate short-term drainage defined as the presence of the stent in the ureter and the lack of surgical or other intervention to treat symptoms associated with the stent itself on the stented side during the first 48 hours [Day 0-2] following placement.
- [Note: In some cases, the ureteral stent may not be sufficient to relieve pain (not associated with stent specifically) and alternative surgical treatment may be warranted. In these cases, patient data will be captured but non-device related cause captured as reason for subject stenting termination.]
- Assessment of retrograde urine reflux after placement of the ureteral stent, as determined by the visualization of urine in the distal ureter to the kidney using cystography after contrast gravity-filling of the bladder and assigning a urinary reflux grade based on:
  - Grade I: urine refluxes into the ureter only.
  - Grade II: urine refluxes into the ureter and up to the kidney without dilation.

- Grade III: urine refluxes into the ureter and kidney and causes mild dilation.
- Grade IV: urine refluxes into ureter and kidney and causes dilation without twisting of the ureter.
- Grade V: urine refluxes into ureter and kidney and causes significant dilation with twisting of the ureter.

- Visualization of distal coil in bladder, after stent placement. Document placement using a cystoscope.

2- Primary safety endpoint:  
Assessment of pain or irritative symptoms (incidence, severity) attributed to the ureteral stent as well as unplanned return visits to ED, OR, or clinic.

3- Secondary endpoint:

- USSQ Scale (Ureteral Stent Symptoms Questionnaire) [Time Frame: Day 3 as endpoint]
- Unplanned hospital visits or doctor visits related to the stent
- Medication use endpoint:
  - Physicians can prescribe standard medications such as alpha blocker (Tamsulosin), Anticholinergic (Oxybutynin), phenazopyridine (Pyridium), ibuprofen and Tylenol prn pain for the duration of the stent plus 1 day (post stent removal) (Document on CRF)
  - Requests for “breakthrough” pain medication (narcotics) would be at the request of the patient post procedure (not to be given as a standard dose). (Document on CRF)
  - Patients to keep medication diary in situations where patients are not taking medications as prescribed

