#### Screening/Enrollment:

- Patients will be screened for eligibility
- If eligible, patients will be enrolled in the study through signing of the Informed Consent Form
- Medical charts will be reviewed, demographics will be collected, and medications will be reviewed prior to surgery

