#### Post-stent Follow-Up:

- Post-operatively complete Ureteral Stent Satisfaction Questionnaire (USSQ) surveys at day 1, day 3, day of stent removal, and 2 days post stent removal (note day of removal) (between 7-10 days in normal practice (even up to 14 days):
- Medications will be tracked on the CRF at day 1, day 3, day of stent removal, and 2 days post stent removal
- Day 1 (12-30 hours after stenting procedure), subject will be evaluated by study personnel for acceptable procedural outcome.
- Document any unplanned hospital visits or doctor visits related to the stent  
Day 1, Day 3, Day of stent removal (i.e., Day 7-10), and 2 days post stent removal, subject will be evaluated by study personnel for ongoing tolerability and stent performance (e.g., drainage) in person or by phone.
- Direct or remote evaluation will be documented. If unusual levels of pain or other potentially serious complications are suspected, the subject will be brought in for Clinician evaluation.

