#### 9.2 SAMPLE SIZE DETERMINATION

At our target enrollment of 50 patients (25 patients in each arm), a power analysis for our primary endpoint (differences in incidence of retrograde urine reflux between randomized study arms) determined that our study will be sufficiently power (80%) to detect a moderate effect size ( $\omega = 0.4$ ) at an alpha level of 0.05.

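### The pre-stent USSQ named in the objectives is neither scheduled nor used: section 9.4.3 plans only an unadjusted comparison, which gives up precision with 25 patients per arm

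*Combined protocol and SAP*

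**What the plan says.** Section 9.4.3, repeating section 9.4.1, states for USSQ that "Mann-Whitney U test or independent t-tests will be used for comparisons of continuous variables", with chi-square or Fisher's exact test for categorical items. It gives no covariate, change score or longitudinal model, and no rule for choosing between the two tests. ANCOVA appears only in the abbreviation list (10.3). Section 9.4.5 gives baseline data a descriptive use only.

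The secondary objectives in section 3 include "Reporting the Ureteral Stent Symptoms Questionnaire (USSQ) before stent placement, after placement at day 3, prior to removal and post removal", and the synopsis (1.1) agrees. The secondary endpoint is fixed as "Time Frame: Day 3 as endpoint".

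The operational sections differ:

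- In the Schedule of Activities (1.3), the row "Ureteral Stent Symptoms Questionnaire" is marked at Day 1, Day 3, stent removal and 2 days after removal. The Screening and Day 0 cells are empty.
- The follow-up plan in section 4.1 lists "surveys at day 1, day 3, day of stent removal, and 2 days post stent removal", all after stenting.
- The screening step in section 4.1 reads "Medical charts will be reviewed, demographics will be collected, and medications will be reviewed prior to surgery", with no USSQ. The Day 0 list has none either.

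**The concern.** Fewer irritative symptoms is one of the two added benefits that section 3 claims for the RELIEF stent, and USSQ is the first secondary endpoint listed. The only power statement in the documents concerns reflux incidence, so nothing shows what the USSQ comparison can detect.

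If symptoms before stenting predict symptoms on Day 3, an unadjusted comparison leaves that variation in the error term. The objectives ask for the measurement that would remove it, but the visit plan does not collect it and the analysis section has no use for it. The two gaps belong together. Correcting the schedule alone would yield a baseline with no role in the test, and correcting 9.4.3 alone would yield a model with no covariate.

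**Working it through.** **Inputs.** From the documents: 25 patients per arm (section 9.2: "At our target enrollment of 50 patients (25 patients in each arm"), 1:1 allocation (4.1), alpha 0.05 and 80% power (9.2, stated for reflux). Assumed: a two-sided test, since sidedness is not stated; no dropout; and the correlation r between pre-stent and Day 3 USSQ. The documents give no USSQ SD, target difference or correlation, so results are in SD units over a range of r.

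**The plan's own figure.** For reflux incidence with w = 0.4 and N = 50, the noncentrality is N × w² = 50 × 0.16 = 8. A 1-df chi-square test at 0.05 then has power 80.7%, which reproduces the stated 80%. The figure says nothing about USSQ.

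**Unadjusted USSQ comparison.**

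- Normal approximation: d = (1.960 + 0.842) × √(2/25) = 2.802 × 0.283 = 0.79 SD.
- Noncentral t with 48 df: d = 0.81 SD.

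**With ANCOVA on the pre-stent score.** The residual SD is multiplied by √(1 − r²) and one df is lost (47 df). The patients needed for the same precision without adjustment are 25/(1 − r²) per arm. Noncentral t, 80% power:

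| r (assumed) | √(1 − r²) | Detectable difference | Variance removed (r²) | Equivalent n per arm | Power at 0.8 SD |
|---|---|---|---|---|---|
| no adjustment | 1 | 0.81 SD | 0% | 25 | 79% |
| 0.2 | 0.980 | 0.79 SD | 4% | 26.0 | 81% |
| 0.3 | 0.954 | 0.77 SD | 9% | 27.5 | 83% |
| 0.5 | 0.866 | 0.70 SD | 25% | 33.3 | 89% |
| 0.7 | 0.714 | 0.58 SD | 49% | 49.0 | 97% |

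At r = 0 the adjusted detectable difference is still 0.81 SD, so the lost degree of freedom costs almost nothing. At r = 0.1 it is 0.805 SD.

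**Chance imbalance.** The between-arm difference in mean baseline score has a standard deviation of √(2/25) = 0.28 SD. As an illustration, an imbalance of 0.5 SD with r = 0.5 would shift the unadjusted Day 3 difference by 0.5 × 0.5 = 0.25 SD. Over repeated randomisations this averages to zero and is already counted in the unadjusted standard error. ANCOVA removes it from the estimate.

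**Which form can be the baseline.** Randomisation and placement are both on Day 0. The earliest scheduled USSQ is on Day 1, 12 to 30 hours after stenting. It can itself be affected by the stent, so adjusting for it could remove part of the effect being estimated. It cannot stand in for a pre-stent form.

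**The case against.** The strongest case against is that a two-sample test is conventional and valid for an unpowered secondary endpoint in a 50-patient trial, and that the benefit rests on an unknown correlation. Both points stand. A low correlation is plausible because Day 3 symptoms may reflect the new stent and the surgery more than the state before them. At r of 0.2 or less the gain is close to nothing, and the r = 0.7 row is not an expected result. What remains is that adjustment costs almost nothing when r is low and helps when it is not.

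Four stronger readings are tempting, and the documents do not support them:

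- *Baseline data are collected and then discarded.* The schedule and visit plan contain no pre-stent USSQ. The fix therefore needs a form as well as a sentence.
- *The plan commits to raw Day 3 scores.* Section 9.4.3 refers only to USSQ findings. Change scores could be compared with the same tests, and the text does not say which is meant.
- *The unadjusted result is biased.* Under 1:1 randomisation it is not, and its type I error is correct.
- *The open choice of test inflates type I error to about 6% or 7%.* Simulation gave 5.8% (normal data) to 6.7% (skewed data), but only if the smaller of the two p-values is always taken. Choosing by a normality test, a more usual reading, gave 5.0% (normal), 5.2% (exponential) and 4.5% (lognormal). Because the trial is open label and states no rule, it is fair to ask for one, but the plan does not imply the worst case.

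**Conclusion.** The point holds as a loss of precision, together with an inconsistency between sections. The pre-stent USSQ required by the synopsis and objectives is missing from the Schedule of Activities and visit plan, and no inferential analysis uses it. With 25 per arm, two-sided alpha 0.05, 80% power and complete data, adjustment would bring the detectable Day 3 difference from 0.81 SD to between 0.79 SD (r = 0.2) and 0.58 SD (r = 0.7), with 0.70 SD at r = 0.5. These sizes depend wholly on the assumed correlation. The validity of the planned comparison is not in question, and the primary reflux analysis is unaffected. The change is worth making because it is cheap and concerns one of the two benefits the trial sets out to show.

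**What to change.** 1. Reconcile the synopsis and secondary objectives with section 1.3 and section 4.1 by adding a USSQ before stenting, at screening or on Day 0. It should be completed before randomisation, since the trial is open label.
2. In sections 9.4.1 and 9.4.3, replace the choice of two tests for the Day 3 USSQ score with one prespecified analysis: ANCOVA of Day 3 USSQ on arm, with pre-stent USSQ as covariate, reporting the adjusted difference with its 95% CI. If a rank-based version is preferred, choose it now and not after seeing the data. Report the other USSQ time points descriptively.
3. State that the Day 1 USSQ is not used as a baseline.

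The cost is one extra questionnaire per patient, one degree of freedom and one sentence of analysis text. A patient with no pre-stent form would drop out of a complete-case ANCOVA, so the text should also say how a missing baseline is handled. If the pre-stent form is not added, the ANCOVA cannot be run. Section 9.4.3 should then still name a single test for Day 3, and the objectives should drop the pre-stent assessment.

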#### 9.4.4 SAFETY ANALYSES

Adverse events and serious AEs will be compared between the two cohorts using descriptive and quantitative statistics, and the data will be presented in a table.

#### 9.4.5 BASELINE DESCRIPTIVE STATISTICS

Baseline descriptive statistics will be performed comparing the two cohorts.

#### 9.4.6 PLANNED INTERIM ANALYSES

N/A

#### 9.4.7 SUB-GROUP ANALYSES

Patients will be randomized to receive either the Relief stent or the current standard stent. Patients will be randomized regardless of age, sex, race/ethnicity or other demographic characteristic since stone disease and stent related pain affects patients of all genders.

#### 9.4.8 TABULATION OF INDIVIDUAL PARTICIPANT DATA

Individual participant data will not be listed by measure/time point; rather the data of the entire cohort will be presented in a de-identified way.

#### 9.4.9 EXPLORATORY ANALYSES

N/A

### 10 SUPPORTING DOCUMENTATION AND OPERATIONAL CONSIDERATIONS

#### 10.1 REGULATORY, ETHICAL, AND STUDY OVERSIGHT CONSIDERATIONS

##### 10.1.1 STUDY DISCONTINUATION AND CLOSURE

This study may be temporarily suspended or prematurely terminated if there is sufficient reasonable cause. Written notification, documenting the reason for study suspension or termination, will be provided by the suspending or terminating party to investigator, funding agency, the Investigational New Drug (IND) or Investigational Device Exemption (IDE) sponsor and regulatory authorities. If the study is prematurely terminated or suspended, the Principal Investigator (PI) will promptly inform study participants, the Institutional Review Board (IRB), and sponsor and will provide the reason(s) for the

termination or suspension. Study participants will be contacted, as applicable, and be informed of changes to study visit schedule.

Circumstances that may warrant termination or suspension include, but are not limited to:

- Determination of unexpected, significant, or unacceptable risk to participants
- Demonstration of efficacy that would warrant stopping
- Insufficient compliance to protocol requirements
- Data that are not sufficiently complete and/or evaluable
- Determination that the primary endpoint has been met
- Determination of futility

Study may resume once concerns about safety, protocol compliance, and data quality are addressed, and satisfy the sponsor, IRB and/or Food and Drug Administration (FDA).

---

#### 10.1.2 CONFIDENTIALITY AND PRIVACY

Participant confidentiality and privacy is strictly held in trust by the participating investigators, their staff, and the sponsor(s) and their interventions. This confidentiality is extended to cover testing of biological samples and genetic tests in addition to the clinical information relating to participants. Therefore, the study protocol, documentation, data, and all other information generated will be held in strict confidence. No information concerning the study or the data will be released to any unauthorized third party without prior written approval of the sponsor.

All research activities will be conducted in as private a setting as possible.

The study monitor, other authorized representatives of the sponsor, representatives of the Institutional Review Board (IRB), regulatory agencies or pharmaceutical company supplying study product may inspect all documents and records required to be maintained by the investigator, including but not limited to, medical records (office, clinic, or hospital) and pharmacy records for the participants in this study. The clinical study site will permit access to such records.

The study participant's contact information will be securely stored at each clinical site for internal use during the study. At the end of the study, all records will continue to be kept in a secure location for as long a period as dictated by the reviewing IRB, Institutional policies, or sponsor requirements.

Study participant research data, which is for purposes of statistical analysis and scientific reporting, will be stored in Redcap. This will not include the participant's contact or identifying information. Rather, individual participants and their research data will be identified by a unique study identification number. The study data entry and study management systems will be secured and password protected.

---

#### 10.1.3 FUTURE USE OF STORED SPECIMENS AND DATA

Data collected for this study will be analyzed and stored at UCSD. After the study is completed, the de-identified, archived data will be stored in RedCap.

---

#### 10.1.5 SAFETY OVERSIGHT

The group of investigators, including the principal investigator and the research support staff will carry out the Data and Safety Monitoring Plan. Data will be reviewed quarterly to ensure that it is accurate, complete, and that its collection is in compliance with the protocol. There will also be a continual assessment of the risks and benefits.

#### 10.1.6 CLINICAL MONITORING

Clinical site monitoring is conducted to ensure that the rights and well-being of trial participants are protected, that the reported trial data are accurate, complete, and verifiable, and that the conduct of the trial is in compliance with the currently approved protocol/amendment(s), with International Conference on Harmonisation Good Clinical Practice (ICH GCP), and with applicable regulatory requirement(s).

#### 10.1.7 DATA HANDLING AND RECORD KEEPING

##### 10.1.7.1 DATA COLLECTION AND MANAGEMENT RESPONSIBILITIES

Data collection is the responsibility of the clinical trial staff at the site under the supervision of the site investigator. The investigator is responsible for ensuring the accuracy, completeness, legibility, and timeliness of the data reported.

All source documents should be completed in a neat, legible manner to ensure accurate interpretation of data.

Hardcopies of the study visit worksheets will be provided for use as source document worksheets for recording data for each participant enrolled in the study. Data recorded in the electronic case report form (eCRF) derived from source documents should be consistent with the data recorded on the source documents.

Clinical data (including adverse events (AEs), concomitant medications, and expected adverse reactions data) and clinical laboratory data will be entered into a Redcap database. The data system includes password protection and internal quality checks, such as automatic range checks, to identify data that appear inconsistent, incomplete, or inaccurate. Clinical data will be entered directly from the source documents.

##### 10.1.7.2 STUDY RECORDS RETENTION

Study documents should be retained for a minimum of 2 years after the last approval of a marketing application in an International Conference on Harmonisation (ICH) region and until there are no pending or contemplated marketing applications in an ICH region or until at least 2 years have elapsed since the

formal discontinuation of clinical development of the study intervention. These documents should be retained for a longer period, however, if required by local regulations. No records will be destroyed without the written consent of the sponsor, if applicable. It is the responsibility of the sponsor to inform the investigator when these documents no longer need to be retained.

#### 10.1.8 PROTOCOL DEVIATIONS

A protocol deviation is any noncompliance with the clinical trial protocol, International Conference on Harmonisation Good Clinical Practice (ICH GCP), or Manual of Procedures (MOP) requirements. The noncompliance may be either on the part of the participant, the investigator, or the study site staff. As a result of deviations, corrective actions are to be developed by the site and implemented promptly.

These practices are consistent with ICH GCP:

- 4.5 Compliance with Protocol, sections 4.5.1, 4.5.2, and 4.5.3
- 5.1 Quality Assurance and Quality Control, section 5.1.1
- 5.20 Noncompliance, sections 5.20.1, and 5.20.2.

It is the responsibility of the site investigator to use continuous vigilance to identify and report deviations within 7 working days of identification of the protocol deviation, or within 7 working days of the scheduled protocol-required activity. Protocol deviations must be sent to the reviewing Institutional Review Board (IRB) per their policies. The site investigator is responsible for knowing and adhering to the reviewing IRB requirements. Further details about the handling of protocol deviations will be included in the MOP.

#### 10.2 ADDITIONAL CONSIDERATIONS

N/A

### 10.3 ABBREVIATIONS

|         |   |
|---------|---|
| AE      | Adverse Event                                       |
| ANCOVA  | Analysis of Covariance                              |
| CFR     | Code of Federal Regulations                         |
| CLIA    | Clinical Laboratory Improvement Amendments          |
| CMP     | Clinical Monitoring Plan                            |
| COC     | Certificate of Confidentiality                      |
| CONSORT | Consolidated Standards of Reporting Trials          |
| CRF     | Case Report Form                                    |
| DCC     | Data Coordinating Center                            |
| DHHS    | Department of Health and Human Services             |
| DSMB    | Data Safety Monitoring Board                        |
| DRE     | Disease-Related Event                               |
| EC      | Ethics Committee                                    |
| eCRF    | Electronic Case Report Forms                        |
| FDA     | Food and Drug Administration                        |
| FDAAA   | Food and Drug Administration Amendments Act of 2007 |
| FFR     | Federal Financial Report                            |
| GCP     | Good Clinical Practice                              |
| GLP     | Good Laboratory Practices                           |
| GMP     | Good Manufacturing Practices                        |
| GWAS    | Genome-Wide Association Studies                     |
| HIPAA   | Health Insurance Portability and Accountability Act |
| IB      | Investigator's Brochure                             |
| ICH     | International Conference on Harmonisation           |
| ICMJE   | International Committee of Medical Journal Editors  |
| IDE     | Investigational Device Exemption                    |
| IND     | Investigational New Drug Application                |
| IRB     | Institutional Review Board                          |
| ISM     | Independent Safety Monitor                          |
| ISO     | International Organization for Standardization      |
| ITT     | Intention-To-Treat                                  |
| LSMEANS | Least-squares Means                                 |
| MedDRA  | Medical Dictionary for Regulatory Activities        |
| MOP     | Manual of Procedures                                |
| MSDS    | Material Safety Data Sheet                          |
| NCT     | National Clinical Trial                             |
| NIH     | National Institutes of Health                       |
| NIH IC  | NIH Institute or Center                             |
| OHRP    | Office for Human Research Protections               |
| PI      | Principal Investigator                              |
| QA      | Quality Assurance                                   |
| QC      | Quality Control                                     |
| SAE     | Serious Adverse Event                               |
| SAP     | Statistical Analysis Plan                           |
| SMC     | Safety Monitoring Committee                         |
| SOA     | Schedule of Activities                              |
| SOC     | System Organ Class                                  |
| SOP     | Standard Operating Procedure                        |

|    |                       |
|----|-----------------------|
| UP | Unanticipated Problem |
| US | United States         |

